11.3.12 Specular Microscopy

Endothelial cell density will be assessed using specular microscopy performed on the central cornea for each eye at Screening, Week 12, Week 28, Week 44, Week 52, and Month 20/Exit. At each examination, average endothelial cell density for each eye will be reported by reading center and used for analysis.

Endothelial cell density baseline and changes from baseline, and raw values will be summarized descriptively by visit for each treatment group in study eyes and pooled for the fellow eyes.

In addition, the number and percentage of patient eyes who reported 1) within ± 200 cells/ mm^2 change; 2) $\geq 10\%$ loss; 3) $\geq 20\%$ loss; 4) $\geq 30\%$ loss; 5) $\geq 40\%$ loss; and 6) $\geq 50\%$ loss in endothelial cell density will be summarized by visit for each treatment group in study eyes and pooled for fellow eyes respectively for each category.

Fellow eye-adjusted endothelial cell density changes from baseline and percent loss from baseline values in the study eye are defined below.

- Fellow eye-adjusted endothelial cell density change from baseline (CFB_ADJ) is defined as the difference in endothelial cell density change from baseline between the study eye and the fellow eye, and calculated as $CFB_ADJ = CFB_SE - CFB_FE$, where CFB_SE is endothelial cell density change from baseline in the study eye and CFB_FE is endothelial cell density changes from baseline in the fellow eye.
- Fellow eye-adjusted endothelial cell density percent loss from baseline (PLoss_ADJ) is defined as the difference in endothelial cell density percent loss from baseline between the study eye and the fellow eye, and calculated as $PLoss_ADJ = PLoss_SE - PLoss_FE$, where PLoss_SE is endothelial cell density percent loss from baseline in the study eye and PLoss_FE is endothelial cell density percent loss from baseline in the fellow eye.

Fellow eye-adjusted endothelial cell density will be summarized descriptively by visit for each treatment group, and the number of patients who reported changes within ± 200 cells/mm² will also be summarized.

Additionally, the number and percentage of patients who reported 1) $\geq 10\%$ loss; 2) $\geq 20\%$ loss; 3) $\geq 30\%$ loss; 4) $\geq 40\%$ loss; and 5) $\geq 50\%$ loss in fellow eye-adjusted endothelial cell density percent loss will be summarized by visit for each treatment group for each category, respectively.

Coefficient of variation (COV) from specular microscopy baseline and changes from baseline, and raw values will be summarized descriptively by visit for each treatment group in study eyes and pooled for the fellow eyes. Fellow eye-adjusted COV will also be summarized descriptively by visit.

Similar analysis will be conducted on pleomorphism (HEX) from specular microscopy.

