11.3.5 Biomicroscopy and Ophthalmoscopy

Biomicroscopy will be performed in each eye by slit-lamp examination at each scheduled visit. Dilated ophthalmoscopy (including vitreous, optic nerve, macula, and retina periphery) and lens status assessment will be performed for each eye at Screening, Baseline, Week 12, Week 28, Week 44, Week 52, and Month 20/Exit.

All biomicroscopy and ophthalmoscopy examinations findings will be coded using MedDRA dictionary.

The number and percentage of patient eyes with biomicroscopy and ophthalmoscopy findings more than 1 severity grade increase (worsening, i.e., a change from 0 to 2 and above, or from 0.5 to 2 and above, or from 1 to 3 and above) from baseline for findings with a severity grade, or a status change from absence at baseline to presence at follow-up visit for findings under other pathology which is not associated with a severity grade, at 1 or more postbaseline visits, will be tabulated by preferred term in descending order of incidence rate. The number and percentage of eyes with any clinically significant findings will be presented (as "Overall") by treatment group for study eye and pooled for fellow eye. Similar analyses will be performed for each treatment cycle and may be provided for findings with other severity grade increase.

At follow-up visits, the lens opacity will be assessed only for eyes evaluated as phakic at baseline. The presence and severity of nuclear, cortical, and posterior subcapsular cataract lens opacities using a 3-point scale (absent, < standard photo #2, and \geq standard photo #2) will be summarized by treatment group for study eye and pooled for fellow eye by visit. The lens status will be presented as data listings and may be summarized with frequency and percent as necessary.

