16.0 DATA HANDLING CONVENTIONS

16.1 VISIT TIME WINDOWS

For all analyses, all follow-up visits or the exit visit will be reassigned with the visit number based on the study days according to the following windows in [Table 16-1](#).

Table 16-1 Visit Time Windows

[figure not shown]
[figure not shown]

Table 16-1 **Visit Time Windows**

If the assessment date (if the assessment date is unavailable, use visit date instead) is on or after the date of the first dose of study treatment, the study day is calculated by assessment date – date of the first dose of study treatment + 1. If the assessment date is before the date of the first dose of study treatment, the study day is calculated by assessment date – date of the first dose of study treatment. Therefore, a negative day indicates a day before the start of the study treatment.

If both scheduled and unscheduled visits occur within a single window, the scheduled visit will be used; and unscheduled visits will be used only if there is no scheduled values available in that window. If multiple visits are eligible for windowing within a single visit window, the visit closest to the target day will be used in the analysis.

If 2 visits are equidistant to the target day, the later visit will be used.

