16.3 REPEATED OR UNSCHEDULED ASSESSMENTS OF SAFETY PARAMETERS

If a patient has repeated assessments before the start of the first treatment, unless otherwise stated, the results from the final nonmissing assessment made prior to the start of the study treatment will be used as baseline. If end-of-study assessments are repeated or if unscheduled visits occur, the last nonmissing postbaseline assessment will be used as the end-of-study assessment for generating summary statistics. However, all postbaseline assessments will be used for safety evaluation, and all assessments will be presented in the data listings.

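### Endothelial cell density loss is tabulated by visit only, so no planned table gives the proportion of treated eyes that ever reached each loss level

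*SAP*

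**What the plan says.** SAP 11.3.12 schedules specular microscopy "for each eye at Screening, Week 12, Week 28, Week 44, Week 52, and Month 20/Exit", which gives five readings after baseline. For raw values it sets five thresholds (10%, 20%, 30%, 40% and 50% or more) and states that "loss in endothelial cell density will be summarized by visit for each treatment group in study eyes and pooled for fellow eyes respectively". For the version that subtracts the fellow eye's change, it states that "loss in fellow eye-adjusted endothelial cell density percent loss will be summarized by visit for each treatment group for each category, respectively". The section plans no worst-value, any-visit or time-to-event summary and states no denominator.

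Other ocular measures are treated differently. SAP 11.3.2 summarizes the worst change in visual acuity across follow-up. SAP 11.3.3 counts eyes whose visual field became abnormal at any follow-up visit. SAP 11.3.4 counts worsened hyperemia at any follow-up visit. Under SAP 11.3.5, findings present "at 1 or more postbaseline visits, will be tabulated by preferred term in descending order of incidence rate". SAP 11.3.7 counts patients whose implant touched the corneal endothelium at any visit within a cycle.

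On data handling, SAP 16.1 says that "all follow-up visits or the exit visit will be reassigned with the visit number based on the study days" and that "unscheduled visits will be used only if there is no scheduled values available in that window". SAP 16.3 says that "all postbaseline assessments will be used for safety evaluation". Where end-of-study assessments are repeated or unscheduled visits occur, 16.3 adds that "the last nonmissing postbaseline assessment will be used as the end-of-study assessment for generating summary statistics".

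**The concern.** Endothelial cell loss is the safety variable most closely tied to an implant lying in the anterior chamber. Protocol 1.3.1 reports that monkeys did not tolerate the implant because of chronic contact with the corneal endothelium, and SAP 11.1 makes corneal events a category of special interest. A reader of the results will want to know what proportion of treated eyes ever lost 20% or more. By-visit percentages cannot be added up to give this, because different eyes contribute at different visits. Implant contact would be reported as a per-cycle any-visit count, while the cell loss it might cause would not be reported in any cumulative form.

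The gap matters most if eyes with loss leave follow-up sooner. Protocol 5.10 allows re-administration to be withheld because of adverse events or safety concerns. Protocol 8.8 and 8.9 let patients who miss an administration leave 12 months after their last one. That is about Week 52 after one administration, and about Week 68 (16 + 52, roughly Month 16) after two. Both fall before Month 20.

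**Working it through.** **Figure to reproduce.** There is none. The documents state no endothelial loss rate, no leaving rate linked to loss, and no denominator. The figures below are illustrations on stated assumptions.

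**1. By-visit rate against the proportion ever affected.** From the documents: 170 eyes per group (Protocol 7.7) and five readings (SAP 11.3.12). Assumed:
- a 10% underlying risk of crossing a threshold, spread over five equal intervals;
- loss persists once reached;
- unaffected eyes leave at 2% per interval;
- affected eyes leave at rate q per interval, after the reading that showed the loss.

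The risk per interval is h = 1 − 0.90^(1/5) = 2.09%. An eye stays measured and unaffected from one interval to the next with probability r = 0.98 × (1 − 0.0209) = 0.9596.

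Ever affected = 170 × h × (1 + r + r² + r³ + r⁴) = 170 × 0.0209 × 4.61 = 16.3 eyes, and 16.3/170 = 9.6%.

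Unaffected eyes measured at the last visit = 170 × 0.98⁴ × 0.90 = 141.1. Affected eyes still measured follow X(k) = X(k−1) × (1 − q) + new cases at k.

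| Affected eyes leaving per interval (q) | Affected eyes at last visit | Last-visit rate | Ever affected |
|---|---|---|---|
| 0% | 16.3 | 16.3/157.5 = 10.4% | 9.6% |
| 2% (same as other eyes) | 15.7 | 15.7/156.8 = 10.0% | 9.6% |
| 5% | 14.7 | 14.7/155.9 = 9.5% | 9.6% |
| 25% | 9.7 | 9.7/150.9 = 6.5% | 9.6% |
| 50% | 6.0 | 6.0/147.2 = 4.1% | 9.6% |

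With assumed risks of 5% and 20% (ever affected 4.8% and 19.3%), the last-visit rate runs from 5.2% down to 2.0%, and from 20.7% down to 8.6%, as q rises from 0% to 50%.

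A simulation built differently agrees. It spreads first losses evenly over the five readings and assumes 15% background loss to follow-up. With no excess leaving, Month 20 shows 10.0% against 9.4% at any visit. If half of the affected eyes are not measured again, the highest by-visit figure is 6.2% against 9.3%.

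**2. Noise in an any-visit count.** Percent loss carries the error of both the baseline and the follow-up reading. For an unchanged eye with per-reading error s and threshold t, the chance of crossing at one reading is Φ(−t / (s√(1 + (1 − t)²))).
- Raw, t = 10%, s = 5%: Φ(−0.10/0.0673) = Φ(−1.49) = 6.9%. Simulated over any of five readings: 22.7%.
- Raw, t = 10%, s = 3%: Φ(−0.10/0.0404) = Φ(−2.48), about 0.7%. Any of five: 2.9%.
- Raw, t = 20%, s = 5%: Φ(−0.20/0.0640) = Φ(−3.12) = 0.09%. Any of five: 0.4%.
- Fellow-eye-adjusted loss combines four readings, so its SD is about s√4 = 2s. At s = 5% and t = 10%, one reading crosses with probability Φ(−0.10/0.10) = 15.9%. Any of five: 41.5%, and 8.6% at t = 20%. At s = 3% and t = 10%, any of five is 16.1%.

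A plain any-visit count of raw loss is therefore informative from 20% upwards. It can mislead in the 10% category, and in the adjusted version at 20% as well.

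**The case against.** A reader might infer that the plan understates a cumulative rate. It does not, because it plans none: each by-visit percentage is correct for its label. With no excess leaving, the last-visit rate is, if anything, slightly higher than the proportion ever affected.

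A reader might also infer that eyes found at an unscheduled visit, or eyes that leave, drop out of the record. The documents do not support that. Under SAP 16.1 an unscheduled reading is displaced only by a scheduled one in the same window, and that reading would show a loss that persists. An eye that leaves still counts at the visit where its loss was measured. Protocol 8.8 asks for the Month 20/Exit procedures at early exit, and 8.9 keeps patients who miss an administration under follow-up for 12 months. Protocol 3 ties early exit to the absence of safety concerns, a condition that 8.8 does not repeat. SAP 16.3 lists every assessment and uses the last nonmissing value as end of study. Sections 16.1 and 16.3 can be read together, with windows governing by-visit tables and 16.3 governing the wider safety evaluation.

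There is already much corneal reporting: by-visit change, pachymetry, corneal adverse events by cycle, and endothelial contact by cycle. Nor is cell density the only measure reported by visit; the cup/disc ratio (SAP 11.3.6) is too.

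All of this stands. It limits the point but does not fill the gap. Corneal adverse events depend on investigator reporting and are not cell-density thresholds. SAP 16.3 names no cell-density table that uses all readings. How exit readings enter the Month 20 row cannot be checked, because Table 16-1 is not shown.

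**Conclusion.** The point holds as a reporting gap. The proportion of treated eyes that ever reached each loss level is absent from the planned tables and cannot be recovered from them. The SAP does provide a worst-change, any-visit or per-cycle count for five other ocular measures.

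The last-visit rate would mislead as a stand-in only if eyes with loss leave faster than others, assuming loss persists once reached. The protocol's rules on re-administration and early exit make that plausible, but no document shows that it happens or how often. The illustrated shortfall (6.5% or 4.1% against 9.6%) rests entirely on assumed leaving of 25% or 50% per interval and is not an estimate for this trial. The consequence is limited to what can be concluded about an implant-specific safety risk.

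**What to change.** Keep the by-visit tables. In SAP 11.3.12 add:

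- For raw study-eye loss, by treatment group, the number and percentage of treated eyes with loss of 20%, 30%, 40% and 50% or more at any postbaseline reading (scheduled, unscheduled or exit), and the same at the last available reading.
- As denominator, all treated eyes with a baseline and at least one later reading.
- For the 10% category, and for any fellow-eye-adjusted version, a count only of loss confirmed at a second consecutive reading or present at the last reading.
- A statement that the windowing rule in 16.1 does not apply to these counts, in line with 16.3.

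The cost is SAP wording and a few descriptive tables. The data will exist, since Protocol 6.2 has all additional images read by the Reading Center. Some noise remains. Loss at the last reading is itself a single reading, so at 5% error the confirmed counts at 10% cannot fall below about 6.9% (raw) or 16% (adjusted) of unchanged eyes. The noise affects Control equally, so these counts should be read as a comparison between groups.

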4.5 Permissible and Prohibited Medications/Treatments

4.5.1 Permissible Medications/Treatments

The fellow eyes of patients randomized to the Bimatoprost SR or Control groups will receive timolol BID for IOP lowering.

Intermittent use of artificial tear products is allowed if they are not taken ≤ 15 minutes before any study procedure or ≤ 15 minutes before or after topical administration of study medication. Intermittent use of ocular decongestants or antihistamines is allowed if not taken within 2 days prior to a scheduled visit and/or ≤ 15 minutes before or after topical administration of study medication. Use of artificial tear products and ocular decongestants or antihistamines may be restarted 3 days after any Bimatoprost SR (or Sham) administration procedure.

Use of postoperative topical ocular antibiotics, corticosteroids, and non-steroidal anti-inflammatory drugs (NSAIDs) from the Administration Day (on Day 1, Week 16, and Week 32) to Day 7 following administration is allowed.

Systemic beta-blocker containing medications are permitted, provided that the dose/dosing regimen has remained stable for at least 2 months prior to Screening, and is not anticipated to change during the duration of the study.

Required surgical procedures may be performed in the fellow eye only after completion of Week 52.

In addition, therapy considered necessary for the patient's welfare may be given at the discretion of the investigator. If concurrent medications may have an effect on study outcomes, these medications should be administered in dosages that remain constant throughout the entire duration of the study. If the permissibility of a specific medication/treatment is in question, please contact Allergan.

The use of systemic NSAIDs is also permitted.

In the unlikely event that the Bimatoprost SR implant requires removal for significant safety reasons, this may be performed at the discretion of the investigator following a discussion with the medical safety physician at Allergan (see Protocol Procedure Manual for details).

Note that in the event that the investigator performs an unanticipated incisional surgical procedure on the study eye during which ocular fluid is to be removed, ocular fluid/implant samples may be collected for analysis (see Protocol Procedure Manual for further details) at the investigator's discretion.

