4.5.2 Prohibited Medications/Treatments

The decision to administer a prohibited medication and/or treatment is done with the safety of the study participant as the primary consideration. When possible, Allergan should be notified before the prohibited medication/treatment is administered.

During the study, patients should not participate in other investigational drug or device studies.

Nonstudy IOP-lowering Medications

Use of any topical ophthalmic medication containing an ocular antihypertensive, other than use of study medication (timolol) in Control group or fellow eyes, is prohibited as concurrent therapy in either eye, unless necessary for the safety of the patient due to inadequate control of IOP as determined by the investigator. Inadequate control of IOP should be confirmed at a subsequent visit (scheduled or unscheduled visit). Prior to Week 52, the investigator will be expected to attest to the need for additional nonstudy IOP- lowering medication for safety reasons. After the Week 52 visit, nonstudy topical IOP-lowering medications will be permitted if in the investigator's clinical judgment the IOP is not adequately controlled at two consecutive visits. Initiation of medication in one eye should not automatically lead to initiation of medication in the other eye. Each eye should be evaluated on an individual basis when determining the need for additional nonstudy IOP-lowering medications. If nonstudy IOP-lowering medication is initiated prior to Week 52, the investigator will be expected to attest to the need for additional nonstudy IOP-lowering medication for safety reasons for each eye individually.

Contact Lenses

Use of soft contact lenses within 3 days and use of rigid gas permeable or hard contact lenses within 1 week prior to a scheduled study visit or Administration Day, or use of contact lenses of any kind within 1 week following any Bimatoprost SR (or Sham) administration in either eye is prohibited.

Contact lenses should be removed prior to instilling any study-provided eye drops and patients should wait at least 15 minutes before putting contact lenses back in the eyes after instilling topical drops.

Other Medications

The following medications (or classes of medications) and treatment procedures are not permitted as concurrent therapy during the study through 12 months after the last Bimatoprost SR or Sham administration unless the patient has already been treated with nonstudy IOP-lowering medication in both eyes:

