[figure not shown]
- Subconjunctival, sub-Tenon's, intravitreal, or other ophthalmic injections of any medications in either eye
- Surgical procedures that are not related to Bimatoprost SR (or sham) administration procedures in the study eye (surgical procedures are allowed in the fellow eye after Week 52 as described in Section 4.5.1)

- Use of any topical ophthalmic medications (except as described above and in Section 4.5.1) in either eye.
- Use of any ophthalmic (including topical, intravitreal, sub-Tenon's, subconjunctival) corticosteroids in either eye from 2 months prior to the baseline visit through 12 months after the last administration, except for use of postoperative topical ocular corticosteroids after administration as described in Section 4.5.1.
- Oral, intramuscular, or intravenous corticosteroids from 2 months prior to the baseline visit through the twelfth month after the last injection.
- Use of LATISSE[®] (bimatoprost for hypotrichosis) during the study period in either eye
- Systemic use of carbonic anhydrase inhibitors (eg, Diamox[®])
- Any initiation of or alterations in systemic regimen of beta-blocker containing medications from 2 months prior to Screening through the final study visit

4.5.3 Definition of Females of (Non-)Childbearing Potential and/or Acceptable Contraceptive Methods

[figure not shown]
For purposes of this study, women will be considered of childbearing potential unless they are naturally postmenopausal or permanently sterilized (ie, hysterectomy). Natural menopause is defined as the permanent cessation of menstrual periods, determined retrospectively after a woman has experienced 12 months of amenorrhea without any other obvious pathological or physiological cause. For women of childbearing potential who may participate in the study, the following methods of contraception, if properly used, are generally considered reliable: hormonal contraceptives (ie, oral, patch, injection, implant), male condom with intravaginal spermicide, diaphragm or cervical cap with spermicide, vaginal contraceptive ring, intrauterine device, surgical sterilization (bilateral tubal ligation, bilateral salpingectomy), vasectomized partner, or true sexual abstinence (when this is in line with the preferred and usual lifestyle of the subject).

The investigator and each patient will determine the appropriate method of contraception for the patient during the participation in the study.

5. Study Treatments

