Optical Coherence Tomography (OCT): OCT of the macula will be performed to assess macular edema. The same instrument should be used throughout the study for a given patient. See the Protocol Procedure Manual for further details.

Specular Microscopy: Endothelial cell density will be assessed using specular microscopy performed on the central cornea at all sites. The final qualification of central endothelial cell density for study entry will be determined by the Reading Center. Qualification will remain valid for 1 year after Screening in patients who are not enrolled at the time of Screening, if in the investigator's opinion there have been no clinically significant changes occurring in the eye (eg, ocular surgery) during that time. All additional specular microscopy images taken during the study will be assessed by the Reading Center. See the Protocol Procedure Manual for further details. The same instrument should be used throughout the study for a given patient.

Pachymetry: Corneal thickness using ultrasound (contact) pachymetry will be performed on the central cornea. The same instrument should be used throughout the study for a given patient. Contact pachymetry may be performed any time after the Hour 2 IOP measurement. See the Protocol Procedure Manual for further details.

Anterior Segment Optical Coherence Tomography (AS-OCT): AS-OCT measurements will be performed at all sites and a Reading Center will be used to examine angle size for

investigational purposes. See the OCT Image Acquisition manuals from the Reading Center for further details on the use of OCT. In the event that the AS-OCT type as specified in the manuals is not available, a suitable alternative may be approved by Allergan and the designated Reading Center for use. The same instrument should be used throughout the study for a given patient.

Visual Field Examination: Visual field examinations will be assessed using automated perimetry ([REDACTED]

[REDACTED]). The same test methodology must be used throughout the entire study for a given patient.

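### The Month 20/Exit fellow-eye-adjusted endothelial cell loss subtracts any surgical cell loss in the fellow eye, because surgery is allowed there after Week 52 and the SAP has no rule for later readings

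*SAP*

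**What the plan says.** SAP 11.3.12 (Specular Microscopy) schedules endothelial cell density in each eye at Screening, Weeks 12, 28, 44 and 52, and Month 20/Exit. It plans two sets of descriptive summaries.

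- **Unadjusted:** values, changes from baseline, the count within ±200 cells/mm², and the counts at ≥10% to ≥50% loss, by visit. Study eyes are shown by arm and fellow eyes are pooled.
- **Fellow-eye-adjusted:** CFB_ADJ = CFB_SE − CFB_FE for change from baseline, and PLoss_ADJ = PLoss_SE − PLoss_FE for percent loss. The latter "is defined as the difference in endothelial cell density percent loss from baseline between the study eye and the fellow eye". The counts at ≥10% to ≥50% "in fellow eye-adjusted endothelial cell density percent loss will be summarized by visit for each treatment group for each category, respectively". COV is adjusted in the same way, and HEX is to be analysed similarly.

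On surgery, Protocol 4.5.1 states: "Required surgical procedures may be performed in the fellow eye only after completion of Week 52". Protocol 4.5.2 lists unrelated surgery in the study eye among the treatments not permitted until 12 months after the last administration, "unless the patient has already been treated with nonstudy IOP-lowering medication in both eyes". The same list notes that "surgical procedures are allowed in the fellow eye after Week 52 as described in Section 4.5.1".

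On data handling, SAP 16.3 uses every postbaseline assessment for safety evaluation. SAP 10.1 excludes values obtained after an IOP-lowering procedure, but only IOP values. SAP 8.0 places concurrent procedures in listings.

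**The concern.** Subtracting the fellow eye makes sense when that eye shows what would have happened to the study eye without the implant. From Week 52 the protocol no longer protects the fellow eye in that role, while for most patients the study eye stays protected. A cell loss caused by surgery in the fellow eye then enters the adjusted value with a minus sign and lowers the loss reported for the study eye. For an implant safety measure this is the anti-conservative direction.

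Endothelial loss is a natural focus for this product. Protocol 1.3.1 reports that monkeys did not tolerate the implant because of chronic contact with the corneal endothelium, and SAP 11.1 makes corneal events an item of special interest. Month 20/Exit is the only scheduled cell count after Week 52. The higher loss categories may hold few patients, so one misclassified patient can matter.

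The two documents also rest on different premises. The rationale in Protocol 12.3.1 for allowing fellow-eye surgery is that the study is not a paired-eye comparison. SAP 19.1 records that the fellow-eye-adjusted variables, which are a paired-eye comparison, were added in SAP Amendment 1.

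**Working it through.** The plan gives no figure to reproduce here. The check traces the timing and then does arithmetic on the SAP's definition.

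**1. When only the fellow eye may have surgery.** Week 32 is 32 × 7 / 30.4375 = 7.4 months, and adding 12 months gives Month 19.4. After three administrations, and without nonstudy IOP-lowering medication in both eyes, the period runs from Week 52 to about Month 19.4. The next scheduled cell count is Month 20/Exit. Adjusted values at Weeks 12, 28, 44 and 52 precede permitted fellow-eye surgery.

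**2. One patient, percent loss.** Let L be the surgical loss in the fellow eye, in percentage points (assumed). With no other fellow-eye loss, PLoss_ADJ = PLoss_SE − L.

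| Study-eye loss | L | Adjusted loss |
|---|---|---|
| 20% | 0 | 20% |
| 20% | 5 | 15% |
| 20% | 10 | 10% |
| 20% | 15 | 5% |
| 30% | 15 | 15% |

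**3. One patient, cells.** Assume 2,500 cells/mm² at baseline in both eyes.

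- Study eye at 2,000, fellow eye loses 20% (500 cells): CFB_ADJ = −500 − (−500) = 0. The patient counts as within ±200 despite a 500-cell loss.
- Study eye unchanged, fellow eye loses 10% (250 cells): CFB_ADJ = 0 − (−250) = +250. The patient falls outside ±200 although the study eye lost nothing.

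The ±200 count can therefore err in either direction.

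**4. Arm mean.** If a share p of an arm is operated, mean PLoss_ADJ shifts by −p × L. The documents give neither quantity.

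- Lowest assumed values: p = 1%, L = 5, shift −0.05 points.
- Middle: p = 5%, L = 10, shift −0.5 points.
- Highest: p = 10%, L = 15, shift −1.5 points.

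Between two arms the bias in the mean difference is −(p₁L₁ − p₂L₂), which is zero when rate and loss are equal.

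**5. Threshold counts.** Assume a study-eye loss with mean 5 and SD 10, an unoperated fellow-eye loss with mean 1 and SD 4, and independent eyes. The SD of the difference is √(10² + 4²) = 10.77. For an operated patient, P(adjusted loss ≥ 20%) = P(Z ≥ (20 − 4 + L)/10.77):

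| L | z | Probability |
|---|---|---|
| 0 | 1.49 | 6.9% |
| 5 | 1.95 | 2.6% |
| 10 | 2.41 | 0.8% |
| 15 | 2.88 | 0.2% |

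With p = 5% and L = 10, the whole arm goes from 6.9% to 0.95 × 6.87 + 0.05 × 0.79 = 6.6%. With a study-eye mean of 15 it goes from 28.9% to 0.95 × 28.87 + 0.05 × 6.87 = 27.8%. Simulation gave the same arm-level results.

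**6. In patients.** Of 170 per arm, suppose 10% (17) truly have ≥20% loss and 5% of those have an operated fellow eye. That is 17 × 0.05 = 0.85 patients. With 20% (34) it is 1.7.

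**The case against.** The strongest reply is that no study-eye loss disappears from the report. A reader might infer that the plan conceals implant-related cell loss. The documents do not support that: the unadjusted study-eye tables use the same loss categories at the same visits, and fellow-eye surgery cannot change them. A study eye with 20% loss still appears in the unadjusted ≥20% row at Month 20/Exit. The adjusted tables are a second descriptive display on which no hypothesis test rests. This stands, and it limits the point to the adjusted tables.

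Three further limits also stand.

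- Only one visit is exposed. Week 52 already falls 20 weeks after the third administration.
- Fellow eyes in all arms receive sham plus timolol under the same surgery rule, so a biased mean comparison between arms does not follow unless surgical rates or losses differ.
- The permission covers required surgical procedures in general. Procedures that do not enter the eye need not cost cells, so intraocular surgery is the relevant subset.

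Two other inferences go too far.

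- Protocol 6.2 might be read as saying that surgery invalidates a cell density reading. The condition that "there have been no clinically significant changes occurring in the eye (eg, ocular surgery) during that time" concerns how long a screening qualification lasts for patients not yet enrolled. It does not address on-study readings.
- The study-eye surgery bar lifts after nonstudy IOP-lowering medication in both eyes, so later surgical loss could be attributed to the implant. That error runs toward reporting harm, and Protocol 7.3.4 plans a separate summary of safety events after such medication starts. It justifies a flag and no more.

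Finally, table specifications sit in a separate document and the content of SAP Table 16-1 is not available here, so a handling rule elsewhere cannot be excluded. None appears in the protocol or SAP text.

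**Conclusion.** The point holds in a limited form. For patients with intraocular fellow-eye surgery before Month 20/Exit, the definition in SAP 11.3.12 subtracts any surgical cell loss in full. This understates the within-arm adjusted means and the ≥10% to ≥50% counts at that visit, and can distort the ±200 cells/mm² count. Adjusted COV and HEX at that visit draw on the same operated eyes.

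The effect is large for an affected patient and small for an arm. With 5% operated and a 10-point surgical loss, the mean moves by 0.5 points and the ≥20% share by about 0.3 to 1.1 points, depending on the assumed study-eye loss. The surgery rate, the surgical loss and the loss distributions are all assumptions, so these figures show scale and predict nothing. The change is still worth making because the bias runs in the reassuring direction on a key safety measure and is cheap to remove.

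**What to change.** In SAP 11.3.12:

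1. State that fellow-eye-adjusted cell density, COV and HEX are not computed from fellow-eye measurements taken after intraocular surgery in that eye.
2. Report by arm the number of patients without an adjusted value for this reason.
3. Keep all values in the unadjusted study-eye and pooled fellow-eye summaries, and flag eyes (study or fellow) that have had intraocular surgery.
4. Give the adjusted table with all values included as a sensitivity analysis.

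The cost is SAP wording and one derivation flag from concurrent-procedure data already collected. A few patients would have no adjusted value at Month 20/Exit. No clinical rule in the protocol changes, and no safety value leaves the unadjusted summaries.
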